 - a. Blinded CGM (Guardian Link (3) Transmitter and Guardian Sensor (3)) will only be worn at baseline, 3 months, and 6 months (two weeks of sensors use). There will be N=140.

Cohort 2: MDI

The Study Period: After completion of the run-in period, subjects with MDI therapy (minimum of N=280) will be randomized and placed into one of 2 different arms during the study period:

- 1. The HCL Arm will use the MiniMed system (i.e., using Auto Mode) for 6 months during the study period. There will be N=140 for the HCL arm.
- 2. The Control Arm will be using their current insulin therapy (MDI).

The Multiple Daily Injection (MDI) subjects will remain on MDI therapy with subjects using their own insulin for 6 months during the study period. The Sponsor will not provide insulin. Blinded CGM (Guardian Link (3) Transmitter and Guardian Sensor (3)) will only be worn at baseline, 3 months and 6 months (two weeks of sensors use). There will be N=140.

MDI subjects who are currently using CGM, i.e. Dexcom or Medtronic Guardian Connect or who are currently using a SMBG alternative, i.e. Libre, will be allowed to enroll in the study and continue using their own device. There will be N=100

Cohort 3: SAP

The Study Period: After completion of the run-in period, subjects with SAP

[figure not shown]
CEP304 Clinical I	CEP304 Clinical Investigation Plan						
CEP304DOC	Revision	Н	Page 24 of 182	Medtronic			

therapy (minimum N=280) will be randomized and placed into one of 2 different arms during the study period. Sensor insertion placement will be according to User guide:

- 1. The HCL Arm will use the MiniMed system (i.e., using Auto Mode) for 6 months during the study period. There will be N=140 for the HCL arm.
- 2. The Control Arm will be using SAP therapy using the MiniMed System.
 - a. The Sensor Augmented Pump (SAP) subjects will use the MiniMed System (SAP without Low Management Suspend on Low, Low Management Suspend before low or Auto Mode) with Real Time CGM for the 6 month study period. There will be N=140.

The Continuation Period: All subjects above will enter the continuation period for 6 months using the MiniMed system with Auto Mode on.

CEP304 Clinical Investigation Plan CEP304DOC Revision H Page 25 of 182 Medtronic

[figure not shown]
CEP304 Clinical Investigation Plan CEP304DOC Revision Н Page 26 of 182 Medtronic

Age at time of screening:					

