The Run-In Period: Following successful screening, all subjects (CSII, MDI or SAP) will enter the run-in period and collect blinded CGM data while using their own diabetes therapy. Blinded CGM consists of using a Guardian Sensor (3) connected to a Guardian Link (3) transmitter. A total period of 2 weeks of CGM data will be collected.

Cohort 1: CSII

The Study Period: After completion of the run-in period, subjects with CSII therapy (minimum N= 280) will be randomized and placed into one of 2 different arms during the study period:

1. The HCL Arm will use the MiniMed system (i.e., using Auto Mode) for 6 months during the study

CEP304 Clinical				
CEP304DOC	Revision	Н	Page 55 of 182	Medtronic

period. There will be N=140 for the HCL arm.

- 2. The Control Arm will use the MiniMed Pump without CGM.
 - a) Blinded CGM (Guardian Link (3) Transmitter and Guardian Sensor (3)) will only be worn at baseline, 3 months, and 6 months (two weeks of sensors use). There will be N=140.

Cohort 2: MDI

The Study Period: After completion of the run-in period, subjects with MDI therapy (minimum of N=280) will be randomized and placed into one of 2 different arms during the study period:

- 1. The HCL Arm will use the MiniMed system (i.e., using Auto Mode) for 6 months during the study period. There will be N=140 for the HCL arm.
- 2. The Control Arm will be using their current insulin therapy (MDI)

The Multiple Daily Injection (MDI) subjects will remain on MDI therapy with subjects using their own insulin for 6 months during the study period. The Sponsor will not provide insulin. Blinded CGM (Guardian Link (3) Transmitter and Guardian Sensor (3)) will only be worn at baseline, 3 months, and 6 months (two weeks of sensors use). There will be N=140.

MDI subjects who are currently using CGM, i.e. Dexcom or Medtronic Guardian Connect or who are currently using a SMBG alternative, i.e. Libre, will be allowed to enroll in the study and continue using their own device. There will be N=100

Cohort 3: SAP

[figure not shown]
The Study Period: After completion of the run-in period, subjects with SAP therapy (minimum N= 280) will be randomized and placed into one of 2 different arms during the study period. Sensor insertion placement will be according to User guide:

- 1. The HCL Arm will use the MiniMed system (i.e., using Auto Mode) for 6 months during the study period. There will be N=140 for the HCL arm.
- 2. The Control Arm will be using SAP therapy using the MiniMed System.

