10.1 Overview

Run-In Period Synopsis (Run-in Visits 1-3)

The purpose of the run-in period is to ensure that study subjects are introduced to study devices and to provide blinded CGM data. Subjects will be trained on CGM use and blinded CGM will be used to collect

CEP304 Clinical				
CEP304DOC	Revision	Н	Page 86 of 182	Medtronic

data with each subject's existing diabetes therapy. There is a window of 60 days from the end of Visit 1 to the end of Visit 3 during which time subjects should complete run-in. Subjects will be started on the study pump at Visit 3.

Devices Worn:

- Medtronic CGM (blinded) only
- Depending on age group, sensor is self-inserted by subject or inserted with assistance
- Existing Therapy

Study Period Synopsis

Overview:

The study period is 6 months Subjects will be randomized at the start the study period into 2 arms:

- HCL Arm: Auto Mode feature on the study pump turned ON
- Control Arm: Continue with own therapy for 6 months
 - CSII Cohort: The CSII Cohort will use the MiniMed Pump without Real Time CGM during the 6 month study period. Blinded CGM (Guardian Link (3) Transmitter and Guardian Sensor (3)) will only be worn at baseline, 3 months, and 6 months (two weeks of sensors use)
 - MDI Cohort: The Multiple Daily Injection (MDI) Cohort will remain on MDI therapy with subjects using their own insulin for 6 months during the study period. Blinded CGM (Guardian Link (3) transmitter and Guardian Sensor (3)) will only be worn at baseline, 3 months, and 6 months (two weeks of sensors use).

MDI subjects who are currently using CGM, i.e. Dexcom or Medtronic Guardian Connect

CEP304 Clinical In				
CEP304DOC	Revision	Н	Page 87 of 182	Medtronic

- or who are currently using a SMBG alternative, i.e. Libre, will be allowed to enroll in the study and continue using their own device. There will be N=100
- SAP Cohort: The Sensor Augmented Pump (SAP) Cohort will use the MiniMed Pump (SAP without Low Management Suspend on Low, Low Management Suspend before low or Auto Mode) with Real Time CGM for the 6 month study period

Note: Subjects 2-6 years of age will automatically enter the HCL arm at the end of the run-in period

Study Period Device Procedures for HCL Arm

Devices Worn:

- MiniMed Pump
- Depending on randomization and age group, sensor is self-inserted by subject or inserted with assistance

Calibration Requirements with Study Meter:

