10.10 Subject Exit, Withdrawal or Discontinuation

Subjects may choose to withdraw from the study at any time by notifying investigational center staff of their intent.

If a subject chooses to end his or her study participation or if a subject is removed from the study at the Investigator's discretion, the reason for termination must be documented both in source documents and on the appropriate eCRF. All study devices and supplies must be returned and the return documented both in source documents and on the appropriate eCRF.

Subjects may also be withdrawn from the study at the discretion of the Investigator. A subject will be withdrawn from the study if:

- In the opinion of the Investigator, the subject's health or safety would be compromised by continuing in the study
- In the opinion of the Investigator, it is in the subject's best interest to discontinue participation in the study
- During the course of the study, subject begins participation in another investigational study (drug or device).

CEP304 Clinical Investigation Plan				
CEP304DOC	Revision	Н	Page 107 of 182	Medtronic

- During the study it becomes known that subjects are using own SMBG or system that replaces SMBG
- During the course of the study, subject begins abusing illicit drugs or marijuana.
- During the course of the study subject begins abusing prescription drugs.
- During the course of the study subject begins abusing alcohol.
- During the course of the study subject begins using pramlintide (Symlin), DPP-4 inhibitors, liraglutide (Victoza or other GLP-1 agonists), metformin, canagliflozin (Invokana or other SGLT2 inhibitors).
- During the course of the study, subject begins using hydroxyurea.
- During the course of the study, subject receives red blood cell transfusion or erythropoietin.
- During the course of the study, the subject demonstrates that he/she is not able to comprehend instructions for study procedures, as evaluated by the appropriate research staff.
- During the study, subject repeatedly activates SmartGuard when instructed otherwise (e.g. Auto Mode is turned on in SAP Cohort)
- During the course of the study, subject is taking oral, injectable, or IV glucocorticoids for 3 or more weeks (e.g. oral prednisone daily or weekly glucocorticoid administration)
- During the study, (female) subject becomes pregnant.
- During the study, the subject experiences two severe hypoglycemic episodes

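### Protocol 10.10 requires withdrawal for using a device in place of finger-stick testing and exempts no cohort, although MDI subjects are expressly allowed to keep such a device

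*Protocol*

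**What the plan says.** Protocol 10.10 (Subject Exit, Withdrawal or Discontinuation) starts with a permissive sentence: "Subjects may also be withdrawn from the study at the discretion of the Investigator". The list that follows is introduced in mandatory terms: "A subject will be withdrawn from the study if". One item on it is: "During the study it becomes known that subjects are using own SMBG or system that replaces SMBG". The item is not limited to a cohort, to an arm, or to devices that were not declared.

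The Cohort 2 text says something different. MDI subjects with their own CGM may take part, and so may those "currently using a SMBG alternative, i.e. Libre, will be allowed to enroll in the study and continue using their own device". This appears in the protocol synopsis, in Protocol section 6 (Study Design), in Protocol 10.1 (Overview) and in SAP section 5. In 10.1 it sits under the control-arm instruction "Control Arm: Continue with own therapy for 6 months".

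For Cohort 1 (CSII) the rule is the reverse. Libre users may enroll but may not use Libre during the study (synopsis and section 6, definition of Cohort 1). The same text describes Libre as an alternative to SMBG and not as real-time CGM.

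**The concern.** A site with an MDI subject who wears a Libre has two instructions for that subject, both in chapter 10. Section 10.1 says the device may stay. Section 10.10 says that using such a device ends participation. Sites that resolve this differently would treat identical subjects differently. Protocol 9 of chapter 10 (Deviation Handling, 10.9) counts any failure to follow the protocol as a deviation, so either choice can be written up as one.

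At stake is who contributes to the MDI comparison. Subjects removed before randomization never enter the ITT population, and the cohort then under-represents people who use Libre with injections. Subjects removed after randomization stay in the ITT population but leave before the scheduled 90-day and 180-day visits. Those visits supply the six-month A1C and the two blinded-CGM collections used for the co-primary endpoints. Both co-primary tests must succeed for the cohort to succeed (Protocol 19.1.6).

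**Working it through.** There is no planned figure to reproduce. The check sets the texts side by side.

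1. **Do both texts cover the same device?** The withdrawal item names systems that take the place of SMBG. The Cohort 2 permission names Libre as an SMBG alternative, and the Cohort 1 definition classes it the same way. On the protocol's own vocabulary, Libre falls under both.

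2. **Do they cover the same subjects and time?** The withdrawal item applies during the study and to subjects in general. Section 8.2 counts a subject as enrolled from consent. The permission covers enrolment and continued use, and 10.1 and 10.6 have controls stay on their own therapy through the study period. The two overlap for MDI Libre users throughout run-in and, for controls, for six months more.

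3. **Is an exemption written anywhere?** Not in the list. Another item there gives the sensor-augmented pump cohort as its example, so cohort-specific wording was available. The Cohort 1 ban agrees with the withdrawal item; the Cohort 2 permission does not. The version history places the admission of MDI subjects with concurrent CGM under Revision F and an update of the withdrawal criteria under an earlier entry. A leftover item would explain the clash, but that is inference.

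4. **When would literal enforcement act?**
   - Run-in is done on existing therapy (10.1), and randomization comes only at Visit 3 (10.3). A declared Libre user already meets the condition before allocation, so a site applying the rule as written would remove that subject then, whichever arm would have followed.
   - If a site left the rule aside in run-in and applied it afterwards, the loss would fall mainly on controls, because HCL subjects start the study sensor at Visit 4 (10.3). Early exit then brings a single visit with the Visit 13 requirements, less c-peptide. The visit tables and the missing-data rules are not in the public text.

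5. **How many subjects?** The documents count CGM and Libre users together and give no Libre share. No number affected can be derived.

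**The case against.** The strongest reply is that an ordinary reader would not see a contradiction, for four reasons.

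- The item speaks of use that becomes known, whereas neighbouring items on drugs and alcohol speak of a subject beginning something. That fits the discovery of undisclosed use, and an MDI subject's CGM use is known at entry because it is a stratification factor (Protocol 19.1.4, SAP 7.7).
- Every subject must be willing to do at least four finger sticks a day and to use the study meter (inclusion criteria 7 and 11), and section 15.2 has all subjects using it. A compliant Libre wearer has arguably not replaced SMBG.
- The preceding sentence gives the investigator discretion.
- A specific permission stated four times should prevail over a general item.

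These readings are plausible, and many sites may adopt one. None is written into the item. The list itself is mandatory, and its first two items refer to the investigator's opinion while this one does not. What stands is that this is a wording conflict and that its practical effect may be small.

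The reply is stronger on consequences. A reader might infer that the rule would produce missing outcome data mainly in the control arm. The documents do not support that as the expected result. Literal enforcement acts during run-in, before allocation. One-sided loss needs a site to overlook the rule until randomization and then apply it to controls.

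**Conclusion.** The conflict is real and worth fixing. As written, 10.10 withdraws MDI Libre users whom the Cohort 2 text admits. The conclusion rests on reading the list's mandatory wording at face value and on the protocol's own description of Libre as an SMBG alternative. The likely cost under literal enforcement is recruitment and representativeness of the MDI cohort; imbalance between arms is conditional on late enforcement. The size is unknown. No endpoint, significance level or sample size is shown to be wrong.

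Two stronger inferences should be resisted.

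- **Loss of power.** A figure would need every own-device user to be withdrawn without outcome data, and it would need a design power that the public text does not give.
- **A miscounted MDI cohort.** A reader might set the planned 100 own-device MDI subjects against the equal numbers with and without CGM in Protocol 19.1.4 and conclude that they cannot both hold. The scope of the 100 is not stated. If it refers to one arm of 140, and 30 of the 100 are Libre users counted as without CGM, the arm has 100 − 30 = 70 with CGM and 140 − 70 = 70 without, which is an equal split. The Cohort 1 text does say that Libre is not real-time CGM. The sample-size section (19.1.3) is not in the public text and may settle the count. No error is established there.

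**What to change.** Add to the item in Protocol 10.10: *does not apply to MDI subjects using a CGM or SMBG alternative (e.g. Libre) declared at enrolment, provided they also use the study meter as required.* Keep the item for Cohort 1 and for undeclared use in any cohort.

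The cost is one clause, carried through the usual amendment route (Protocol 22.8), and a note to sites. The public SAP text has no withdrawal list and already carries the Cohort 2 permission, so it needs no matching change. No patients, visits or recruitment targets change.

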11.1 Subject Stopping Rules

- 1. One episode of DKA or 2 episodes of severe hypoglycemia will result in withdrawal of subject from study, regardless of which arm or period they are in.
- 2. The first episode of Severe Hypoglycemia may lead to withdrawal, if it is secondary to subject non-compliance or other individual safety concerns:
 - o Subject is not using the bolus wizard
 - Subject is not checking blood glucose using finger sticks
 - Subject is non-compliant with sensor wear
 - Subject is not following protocol procedures

11.2 Stopping Rules for Entire Study

The study will be stopped if DMC determines that there are significant safety issues. (See DMC section.)

Note: If it is decided to withdraw patients from participation in the study or if the study is stopped, subjects will be followed-up in accordance with standard practice.

12. Safety Success Criteria

In order to achieve safety success, the following study success criteria must be met for the HCL Arm by the end of the study:

CEP304 Clinical Investigation Plan

CEP304DOC Version H Page 110 of 182 **Medtronic**

Table 14. Safety Success Criteria

Adverse Event	Reference	Reference Rate > 25 years old	Reference Rate 15-25 years old	Reference Rate <15 years old	Study Success Criteria
DKA events per 100	STAR 3	SAP arm: 0.68	SAP arm: 2.7	SAP arm: 2.2	4 events per 100
patient years	Bergenstal et. al	Control arm: 0	Control arm: 3.6	Control arm: 0	patient years with HCL
putient years	530 G Adult inhome study CEP 266 (MDT on file)	1.27	3.4	N/A	arm
	530 G Pediatric inhome study CEP 287 (MDT on file)	N/A	N/A	0	
	Type 1 exchange Weinstock et. al	4.8	N/A	N/A	
	Type 1 exchange Cengiz et. al	N/A	9.9	9.9	
Severe hypoglycemia per 100 patient years	STAR 3 Bergenstal et. al	SAP arm: 16.5 Control arm: 20.9	SAP arm: 5.4 Control arm: 3.9	SAP arm: 10.2 Control arm: 3.6	< 8 events per 100 patient years with HCL arm

CEP304 Clinical Investigation Plan

CEP304DOC Version H Page 111 of 182 **Medtronic**

Adverse Event	Reference	Reference Rate > 25 years old	Reference Rate 15-25 years old	Reference Rate <15 years old	Study Success Criteria
	530 G Adult inhome study CEP 266 (MDT on file)	0.85	0	N/A	
	530 G Pediatric inhome study CEP 287 (MDT on file)	N/A	N/A	1.42	
	Type 1 exchange Weinstock et. al	11.8	N/A	N/A	
	Type 1 exchange Cengiz et. al	N/A	6.2	6.2	

CEP304 Clinical				
CEP304DOC	Revision	Н	Page 112 of 182	Medtronic

Descriptive summary (i.e. not statistically powered) for severe hypoglycemia and DKA events rates will be performed between the HCL and control arms for each age group (< 15 years, 15-25 years, and > 25 years), as well as the overall event rates.

Severe hypoglycemia and DKA event rates were taken from the following

- Richard Bergenstal et.al: Effectiveness of Sensor-Augmented Insulin-Pump Therapy in Type 1Diabetes.New England Journal of Medicine, 2010; 363:311-20
- 2. Weinstock et. al: Severe hypoglycemia and diabetic ketoacidosis in adults with type 1 diabetes: results from the T1D Exchange clinic registry. J Clin Endocrinol Metab. 2013 Aug;98(8):3411-9.
- 3. Cengiz et. al: Severe hypoglycemia and diabetic ketoacidosis among youth with type 1 diabetes in the T1D Exchange clinic registry. Pediatr Diabetes. 2013 Sep;14(6):447-54.
- 4. MDT on file: Statistical Analysis Plan (SAP) for CEP304, 056-F286

13. Medical Oversight

In order to conduct the study, staffing with the appropriate training is required:

13.1 Medical Staff

A physician who has managed patients on both CGM and insulin pump will be included in the study as the principal investigator.

13.2 Qualification

The investigator (or designee) will need to have one of the following qualifications; Endocrinology fellowship, management in patients with diabetes in a clinical practice. The provider must be qualified to treat diabetic emergencies.

13.3 Experience

Investigator (or designee) must also have at least one year experience in managing patients with insulin carbohydrate ratios and insulin sensitivity ratios in his/her practice

CEP304 Clinical				
CEP304DOC	Revision	Н	Page 113 of 182	Medtronic

14. Safety Monitoring/Risk Analysis

14.1 Glucose Monitoring Risk

• Subjects will be instructed to use clean fingers when performing finger stick glucose testing. Subjects will be instructed to test 4-6 times a day and also before driving (as applicable). Subjects will have training on diabetes self-management principles.

14.2 Hypoglycemic/Hyperglycemic Risk

• Intervention and treatment for hypoglycemia and hyperglycemia is addressed in Section 16.

14.3 Calibration of CGM Risk

 When an erroneous glucose value is used to calibrate a CGM, the bias is carried through until the next opportunity to re-calibrate the CGM. This can result in an incorrect bias. In order to mitigate this risk, every new sensor will have an initial calibration.

14.4 Reuse Risk

• All study devices (including the Serter) will be single patient use.

14.5 Sterilization Risk

The following devices will be supplied sterilized:

- Infusion sets
- Insulin reservoirs
- Glucose sensors

14.6 Misuse Risk

• Comprehensive training will take place for clinical staff regarding the operation of the HCL, all of its

CEP304 Clinical 1				
CEP304DOC	Revision	Н	Page 114 of 182	Medtronic

functional components and all other study devices to be used during the study at the investigational center initiation visit.

14.7 Risk of Blood Sample Collection, Contamination From Sampling Techniques

Detailed mitigations to blood sampling risk are provided in Section 15.

14.8 A1C Risk

A Central laboratory will be used for A1C testing and a laboratory manual will be provided separately.
 A1C is a primary endpoint. For subjects 2-6 years of age, Point of Care testing is an acceptable alternative.

15. Glucose and Glycemia Measurements

15.1 Glucose and Glycemia Measurements

During the course of the study, the subjects' blood glucose, SG levels, A1C, and blood ketone, will be assessed using the following methods in this section (Section 15).

15.2 Daily Blood Glucose

Values will be assessed during the study by all subjects using the Study Meter. The control solution test will be done following the manufacturer's IFU during Home use. Subjects will be trained on the use of the Study Meter per the manufacturer's instructions for use.

15.3 Blood Ketone Values

Blood ketones will be determined by all subjects using the Ketone Meter during home use. The control solution test will be done following the manufacturer's IFU during Home use. Study staff will be trained on the use of

CEP304 Clinical I				
CEP304DOC	Revision	Н	Page 115 of 182	Medtronic

the Ketone Meter per the manufacturer's IFU. All ketone measurements will be recorded on the appropriate eCRF upon entry into the Log Book section of CareLink Personal for Clinical Research/CareLink Clinical Software.

Note: In the event the blood ketone meter is not used by subjects to collect ketone values, urine ketones must be measured and entered appropriately into CareLink as urine ketones.

